# **Study Population:**

Group A: Hospitalized COVID-19 patients ages ≥18 years with respiratory symptoms, requiring >6L of oxygen to maintain O2 saturation >92%. Patient may not require intubation, and may be admitted for no longer than 14 days.

Group B: Hospitalized COVID-19 patients ages ≥18 years requiring intubation.

Study Duration: May 15, 2020 to December 31, 2022

Study Design: This phase 2 trial will evaluate the efficacy and safety of SARS-CoV-2 convalescent plasma as treatment for confirmed COVID-19 respiratory disease (as defined in the inclusion criteria). Adults 18 years of age and older may participate. Patients may be enrolled in group A within 14 days of admission to the hospital and may be enrolled in group B at any time after intubation. A total of 300 eligible subjects with significant oxygen requirements and 200 eligible subjects who require intubation will be included in the study. They will receive convalescent plasma from either a patient who has recovered from COVID-19 or from an asymptomatic carrier with confirmed IgG against SARS-CoV-2. Subjects will not be randomized but the amount of anti-SARS-CoV-2 IgG and IgA in any unit of plasma will not be known when the unit is assigned to the patient. This will allow us to examine the relationship between the amount of anti-SARS-CoV-2 antibody and outcomes. Analysis will be based on measurement of optical density of the IgG level in the unit of plasma the patient is randomly supplied by the blood bank. While investigators and patients will be aware the patient is receiving a unit of COVID-19 convalescent plasma, both the investigators and the patients will be blinded to the antibody content of that unit.

Assessment in all subjects: Given the issues with the pandemic such as limitations on PPE, and the need for strict isolation, patient data will be limited to that which is acquired from the EPIC EMR (in use at our institution) but not from face to face interview with the patient. The data will be supplemented as possible with phone interview with the patient or their LAR. Consenting will be e-consent based using RedCap with the consent form e-mailed to the patient or the LAR for review prior to the actual consent process. Consent will be obtained over the phone and with a witness: the consent provider and the witness will both document the consent process within the patient's chart in the EPIC EMR.

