# Group B Primary Efficacy Endpoint: Mortality at 28 days.

- Group B Secondary Efficacy Endpoints:
  - **1.** Final outcome on a 7-point ordinal scale
  - **2.** Cardio-circulatory arrest (at any time)
  - 3. Renal failure, as measured by RIFLE criteria
  - 4. Liver failure, as measured by elevation of ALT and AST to 5x the upper limit of normal or significant worsening of current liver failure with rise in transaminases of >25%
  - **5.** Evidence of cytokine storm based on measurement of inflammatory markers
  - **6.** Type and duration of respiratory support
  - 7. Requirement of pressor support
  - 8. ICU mortality
  - **9.** ICU length of stay
  - **10.** In hospital mortality
  - **11.** Length of stay
  - **12.** Days from transfusion till end of ventilator support in survivors
  - **13.** Ventilator-free days
  - 14. Readmission rate
  - **15.** Patient level of anti-SARS-CoV-2 IgG at the following times: prior to transfusion, 1-hour post-transfusion, 24 hours post-transfusion, 72 hours post-transfusion, 7 days post-transfusion, every 7 days until discharge, day of discharge.
  - **16.** Evaluate the rates, levels (based on CT values) and duration of SARS-CoV-2 RNA in nasopharyngeal swabs using RT-PCR amongst the anti-SARS-CoV-2 convalescent plasma at the following times: prior to transfusion, 24 hours post-transfusion, 72 hours post-transfusion, 7 days post-transfusion, and 14 days post-transfusion.

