**Secondary Outcomes:** Analyses of all secondary outcomes will use a 0.3% significance level based on the Bonferroni correction for 16 tests. Final outcome measured on a 7-point ordinal scale will be analyzed using standard linear regression,

although we will also consider proportional odds models should the range of the scale actually used be small (i.e., only 3-4 categories appear in the data). We will not use splines for the standard linear regression, but will use splines if a proportional odds model is fit to the data. We will use the same logistic regression approach as for the primary outcomes for all binary secondary outcomes (cardio-circulatory arrest, renal failure, liver failure, evidence of cytokine storm, pressor support required, and readmission).

We anticipate a small number of total number of mortality events for Group A. Should mortality for Group A be small, we will use Fisher's exact test based on categorizing the unit received by each patient as either low vs. high for amount of Anti-SARS-CoV-2-spike protein IgG. The cutoff for categorizing units will be based on either median amount or based on the cutoff determined by the Bayesian log-binomial piecewise model. For Group B, all secondary mortality outcomes will be analyzed the same as for the primary outcome. Should the number of events for any specific type of mortality (e.g., ICU mortality) prove small, we will use the approach used for analyses of Group A.

We will use a generalized linear model with splines to analyze all duration types of variables (duration of respiratory support, ICU length of stay, total length of stay). We will consider using normal, log-normal, and gamma distributions, along with appropriate links.

Type of respiratory support will be analyzed using a multinomial regression with splines for antibody amount, although we will also consider using Fisher's exact test by categorizing the unit received by each patient as either low vs. high for amount of Anti-SARS-CoV-2-spike protein IgG.

We will use either standard linear regression or Poisson regression for ventilator-free days, including splines.

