Maximum tem	nperature:	Minimu	m tempera	ture:		
Maximum hea	art rate:	 Minimu	m heart rat	e:		
		(based on mean a			MAP:	_
Minimum bloo	od pressure (l	based on mean ar	terial press	ure):	MAP:	_
		on and the method				
		and the method of				
Minimum O 2 s	saturation, O 2	gedelivered, and th	e method o	f delivery:		
Maximum O 2	saturation, O	2 delivered and th	e method o	f delivery:		
Maximum res	piratory rate:	Minimu	m respirato	ry rate:		
Was the patie		ator: Y/N	Proned: Y/	N On N	litrox: Y/N	On ECMO: Y/N
Markers of	Value	Complete Blood	Value	Metabolic	Value	
Inflammation	Value	Count With	Value	Markers	Value	
and Other		Differential		- Trial No. 5		
Ferritin		WBC		Sodium		
Fibrinogen		Hemoglobin		Potassium		
CRP		Hematocrit		Chloride		
ESR		Platelets		CO 2		
CK		Neutrophils		BUN		
D-Dimer		Lymphocytes		Creatinine		
LDH		Monocytes		Glucose		
Interleukin-6		Eosinophils		Total Protein		
				Albumin		
				Globulin		
Triglycerides				Alk Phos		
Procalcitonin				ALT		
				AST		
				Total Bilirubin		
Append any p	ositive micro	, EKG, or echocal biology results for for this date of ho	this date o	f hospitalization	spitalization	
Signature of c	coordinator			Date		
Signature of I		eviewing data		Date		 

ABACCuS Daily Medication	ns Data	Collection	Form:						
Patient Initials/Study ID: Da			Date of Enrollment:						
Study day #: Hospital day #:			]	Date of record: Date data recorded:					
For the calendar day indicate	ed above	e:							
Was the Patient Sedated: Y/	N		Sedation	n Used: _					
Was the Patient Paralyzed: `	Y/N		Paralytic	: Used: _					
Was the Patient on Pressors	: Y/N		Pressors	s Used: _					
Medications Initiated on Th	nis Cale	ndar Day:							
Medication	Dose		Route of Administ		Frequency	1	Time Started		
Madiantiana Diagontinuad	or Com	nloted on T	hie Colond	lor Doy					
Medications Discontinued Medication	or Com	Medication		lai Day.	Medicat	tion			
Medications with Dose Mo	dificati	ons on This	Calendar	Dav:					
		Change		Frequency Change Time			Time of Change		
Append the medication ad	ministra	ation record	d and any b	lood pro	ducts for the	above ca	lendar date		
Signature of coordinator				Da	ite				
Signature of Investigator rev	iewing d	ata		Da	nte				

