	Carron (1) No limitation	ig supplemental asive ventilation	O 2 or high flo	O (4) Req w O 2 device	luiring supp			
Cardio-circulatory an	` '	ys of transfusion	on: Y/N		If so c	late:		
Renal failure by RIFLE criteria within 28 days of trans				Y/N	If so c	date:		
	B days of transfu T or AST >5x three rsening of preex	ne upper limit c			If so o	late:		
Evidence of cytokine	storm based or	n inflammatory	markers:	Y/N	If so c	late:		
Days on ventilator: _	Days off	ventilator:	_ Days o	on coldflov	N:			
Days on CPAP:	Days on I	BIPAP:	Days o	Days on non-rebreather:				
Days on NC:	Days on I	Hiflo NC:	_ Discha	Discharge on new home O 2 : Y/N				
Requirement of pres	sor support: Y/N							
Pressors used	d and dates of u	se:						
In hospital mortality: Length of Stay: Readmission: Y/N	_ ICU Leng	days: Y/N th of Stay:	<del></del>			date:		
	55 4.49			<del> </del>	55 6			
Signature of coordinate	or			Date		-		

Date

Signature of Investigator reviewing data

ABACCuS Final Outcor	me Form Group A:		
Patient Initials/Study ID:		Date of Enrollment:	
Plasma Unit Used:		Date and Time of Transfusion:	
Primary Outcome:			
Was the patient intubated	d after the transfusion: Y/N		
If intubated: Da	ate of intubation:	Study Day #:	
Secondary Outcomes:			
O Hospitalized, O O	int ordinal scale: (1) No limitations on activities (3) Not requiring supplemental O (5) On non-invasive ventilation of (6) On invasive mechanical ventif (7) Deceased	$O(4)$ Re high flow $O_2$ devi	equiring supplemental O 2
Cardio-circulatory arrest after transfusion: Y/N		If so date:	
Renal failure by RIFLE criteria after transfusion: Y/N		If so date:	
	fusion: Y/N or AST >5x the upper limit of e ening of preexisting liver failure		If so date: AST of >25%: Y/N
Evidence of cytokine s	torm based on inflammatory m	arkers: Y/N	If so date:
Days on ventilator:	Days off ventilator:	Days on coldflo	ow:
Days on CPAP:	Days on BIPAP:	Days on non-rebreather:	
Days on NC: Days on Hiflo NC:		Discharge on new home O 2 : Y/N	
Requirement of presso	or support: Y/N		
Pressors used a	and dates of use:		
In hospital mortality: Y/Length of Stay: Readmission: Y/N		_	If so date:
Signature of coordinator		Date	
Signature of Investigator reviewing data		Date

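### The pressor-support endpoint has no onset or baseline rule, so pressor use that was already under way at transfusion may be scored as an event; renal failure shares the gap to a lesser degree.

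*Combined protocol and SAP*

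**What the plan says.** **Endpoint text.** Section 2.1 lists "Requirement of pressor support" and "Renal failure, as measured by RIFLE criteria" among the secondary efficacy endpoints, in the same words for both groups. Neither item says whether a condition present before transfusion counts. The liver item differs: besides a transaminase threshold it covers "significant worsening of current liver failure with rise in transaminases of >25" per cent, which is a rule for patients who already have the condition.

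**Entry.** The Study Design paragraph of the protocol summary says that patients "may be enrolled in group B at any time after intubation". The exclusion criteria in Section 2.3 do not mention pressor use or renal failure at entry.

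**Analysis.** Section 3.1 states: "We will use the same logistic regression approach as for the primary outcomes for all binary secondary outcomes". It names pressor support and renal failure among these outcomes. The primary approach is logistic regression on IgG with age, gender and race. Comorbidities are added one at a time in a sensitivity analysis that is described under the primary outcomes.

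**Forms.** The Final Outcome Form for Group A asks for "Renal failure by RIFLE criteria after transfusion: Y/N", with a date, and the 28 Day Outcome Form for Group A limits the same item to 28 days from transfusion. On both forms the pressor item is a plain yes/no without a window, followed by a request for the agents and dates of use. The Daily Medications form asks "Was the Patient on Pressors" for each calendar day and has a start time for each medication begun that day. The Group B outcome form is not in the supplied text.

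**The concern.** An efficacy endpoint should be an event that the unit of plasma could have prevented. A patient who is on a vasopressor when the transfusion starts has already met a bare requirement for pressor support, whatever the antibody content of the unit. If such a patient is scored as an event, the outcome is fixed before treatment and carries no information about IgG.

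This matters most in Group B, where patients are intubated and may be enrolled late in their illness. The result would be an association drawn towards the null on an endpoint that is already tested at a strict level. A null finding could then be misread as evidence that antibody content has no bearing on haemodynamic support.

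**Working it through.** **The plan's own figure.** The secondary level follows from 0.05 / 16 = 0.003125, which is 0.3% as printed. The plan states no power for the pressor or renal endpoints, so there is none to reproduce.

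**Inputs.** The Group B sample size of 200 (Section 3.2) and the 0.3% level (Section 3.1) come from the plan. The following are assumptions, because the documents do not give them: q, the share already affected at transfusion, taken as independent of the unit's IgG; p, the new-onset risk at low and at high IgG; an even split into 100 low-IgG and 100 high-IgG patients; two-sided testing; and every prevalent case scored as an event.

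**Dilution.** The observed risk is q + (1 − q)p. The observed risk difference is therefore (1 − q)(p_low − p_high).

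With q = 0.50, p_low = 0.50 and p_high = 0.25:
- low IgG: 0.50 + 0.50 × 0.50 = 0.750
- high IgG: 0.50 + 0.50 × 0.25 = 0.625
- risk difference: 0.125 instead of 0.25
- relative risk: 0.625 / 0.750 = 0.83 instead of 0.50

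**Power.** For two groups of n, power = Φ[(d − z·se0) / se1]. Here d is the risk difference, se0 = √(2·p̄(1 − p̄)/n), se1 = √([p1(1 − p1) + p2(1 − p2)]/n), and z = 2.955 for a two-sided level of 0.003125.
- Prevalent cases counted, n = 100: se0 = 0.0656, se1 = 0.0650, and (0.125 − 2.955 × 0.0656) / 0.0650 = −1.06, so power is 14.5%.
- Patients at risk only, n = 50: se0 = 0.0968, se1 = 0.0935, and (0.25 − 2.955 × 0.0968) / 0.0935 = −0.39, so power is 35%.

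With se1 in place of se0 and a level of exactly 0.3% (z = 2.968), the two values are 15% and 38%.

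**Other assumed values** (first formula, level 0.05/16):

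| New-onset risk, low vs high IgG | q | RR, prevalent counted | Power, prevalent counted | Power, at risk only (RR 0.50) |
|---|---|---|---|---|
| 50% vs 25% | 0 | 0.50 | 76% | 76% |
| | 20% | 0.67 | 45% | 63% |
| | 40% | 0.79 | 22% | 45% |
| | 60% | 0.88 | 9% | 25% |
| 40% vs 20% | 0 | 0.50 | 55% | 55% |
| | 20% | 0.69 | 25% | 42% |
| | 40% | 0.81 | 11% | 28% |
| | 60% | 0.90 | 4% | 15% |

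In every row with q above zero, restricting to patients at risk gives more power than counting prevalent cases, although it uses fewer patients.

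**The case against.** The strongest reply is that nothing in the documents says prevalent cases are counted. The endpoint entries are one-line names. The outcome forms ask for dates of pressor use and the daily form records status, so a sensible analyst could derive new onset without changing the protocol. This is right as far as it goes, and it is why the point is worded as *may* be scored. It does not close the gap: no rule directs the analyst to make that derivation, and a plain yes on the pressor item is the most direct reading of the endpoint.

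For renal failure the reply is stronger. The Group A forms place it after transfusion, which points to post-transfusion events. What remains is that failure present at transfusion and continuing afterwards could still be ticked, and that there is no counterpart to the liver item's worsening clause.

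The power figures are also open to challenge. They rest on assumed rates and a two-group comparison, whereas the plan fits splines to continuous IgG. They illustrate direction and order of size only. Even after the fix, power at the 0.3% level stays modest in most of these scenarios.

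A reader might infer three stronger points that the documents do not support:
- *Cardiac arrest has the same fault.* The Group A forms tie arrest to after transfusion, and it is a discrete, dated event. The open-ended wording in Section 2.1 fits the Final Outcome Form, and a 28-day limit would discard later events that this form collects.
- *Chance imbalance in baseline status would pass for an antibody effect.* If baseline status is independent of the unit's IgG, which the blinding makes plausible, the significance level already allows for chance imbalance.
- *Any antibody effect is diluted.* Only these secondary endpoints are involved.

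**Conclusion.** The point holds for pressor support. As written, the plan lets ongoing use score as an event, and the model contains nothing to separate it from new use. If baseline use is independent of the unit's IgG, the risk difference shrinks by exactly (1 − q) and the relative risk moves towards 1. The practical size cannot be computed from the documents; in the hypothetical case with q = 50%, the relative risk is 0.83 instead of 0.50 and power falls by more than half (14–15% against 35–38%).

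Renal failure is affected to a lesser degree: it has a post-transfusion window on the Group A forms but no rule for patients already affected. How Group B outcomes are recorded could not be checked. Intubation in Group A and 28-day mortality in Group B are not touched, so this is a minor point that is worth settling in advance.

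**What to change.** Before the antibody blind is lifted, add a derivation rule to Section 3.1. Pressor support and renal failure are analysed as new onset after transfusion, among patients free of the condition when the transfusion starts. Patients already affected are tabulated separately by IgG level. Because the restriction uses status before transfusion, it does not select on anything the plasma could have changed. For renal failure, also state which RIFLE stage counts and which creatinine is the reference.

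The data are already planned: daily pressor status and medication start times on the Daily Medications form, and a baseline and daily metabolic panel that includes creatinine (Sections 2.2 and 2.4, daily laboratory form). Start times are needed to place events on the day of transfusion before or after the infusion.

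Adding baseline status as a covariate is not a good substitute. If every prevalent case scores yes, the covariate predicts the outcome perfectly in those patients, its coefficient has no finite estimate, and they add nothing to the IgG estimate.

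The cost is a few sentences and a smaller denominator for these two endpoints.

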# **Group A Primary Efficacy Endpoint:** Avoidance of intubation at 28 days. **Group A Secondary Efficacy Endpoints:**

- **1.** Final outcome on a 7-point ordinal scale
- **2.** Cardio-circulatory arrest (at any time)
- 3. Renal failure, as measured by RIFLE criteria
- 4. Liver failure, as measured by elevation of ALT and AST to 5x the upper limit of normal or significant worsening of current liver failure with rise in transaminases of >25%
- 5. Evidence of cytokine storm based on measurement of inflammatory markers
- **6.** Type and duration of respiratory support
- 7. Requirement of pressor support
- 8. ICU mortality
- **9.** ICU length of stay
- **10.** In hospital mortality
- **11.** 28-day mortality
- **12.** Length of stay
- **13.** Ventilator-free days
- **14.** Readmission rate
- **15.** Patient level of anti-SARS-CoV-2 IgG at the following times: prior to transfusion, 1-hour post-transfusion, 24 hours post-transfusion, 72 hours post-transfusion, 7 days post-transfusion, every 7 days until discharge, day of discharge.
- **16.** Evaluate the rates, levels (based on CT values) and duration of SARS-CoV-2 RNA in nasopharyngeal swabs using RT-PCR amongst the anti-SARS-CoV-2 convalescent plasma at the following times: prior to transfusion, 24 hours post-transfusion, 72 hours post-transfusion, 7 days post-transfusion, and 14 days post-transfusion.

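### Group B secondary endpoint 12 measures ventilator time in survivors only, so it is selected on the primary outcome and can show longer ventilation at high IgG with no true effect.

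*Combined protocol and SAP*

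**What the plan says.** Section 2.1 lists item 12 of the Group B secondary efficacy endpoints as "Days from transfusion till end of ventilator support in survivors". It does not say to what date a patient must survive. The same list has two ventilation measures without a survivor restriction: item 6, "Type and duration of respiratory support", and item 13, "Ventilator-free days". Group A has both of these and no survivor-only ventilator endpoint.

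Section 3.1 sets the testing level: "Analyses of all secondary outcomes will use a 0.3% significance level based on the Bonferroni correction for 16 tests". For times it says: "We will use a generalized linear model with splines to analyze all duration types of variables", and its bracketed list of such variables covers respiratory support, ICU stay and total stay. Item 12 is not named there. For item 13 it says: "We will use either standard linear regression or Poisson regression for ventilator-free days, including splines". It does not say how a patient who dies is counted in any of these measures.

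Section 3.2 assumes 28-day survival of 25% at baseline and sizes Group B (n = 200) to detect 50% at high IgG. "ICU mortality", ICU length of stay and readmission are secondary endpoints in both groups, with no stated denominator. Section 2.2 follows patients for readmission for 90 days from discharge.

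**The concern.** Item 12 can be computed only in patients who live, and the trial is designed on the premise that high IgG doubles that proportion. The survivors above and below the IgG threshold are then different kinds of patient. Those above include people who would have died with a low-IgG unit. If these were the sicker patients, they probably also needed longer ventilation. The comparison then attributes their longer course to the antibody level.

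The distortion grows with the mortality benefit, so item 12 is least reliable when the primary analysis succeeds. The Bonferroni level does not address it, because this is bias and not chance. A reader of the results could see better survival reported beside apparently slower weaning and take the second as a harm.

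**Working it through.** **The plan's own figures.** Secondary level: 0.05/16 = 0.003125, which rounds to the stated 0.3%. Power for 25% versus 50% survival with n = 200 is stated as 87.8%. The documents give the threshold (5) but not the IgG distribution. With IgG assumed uniform on 0 to 10 and a linear logistic model, two simulation runs gave 87.8% and 89.2%. Other assumed distributions gave 68% to 87%. The stated power is plausible, and it is used here only as the source of the two survival rates.

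**Inputs for the bias.** From Section 3.2: n = 200, survival 25% and 50%, threshold 5. Assumed: IgG uniform on 0 to 10, so about 100 patients on each side. Expected survivors are 100 × 0.25 + 100 × 0.50 = 75. Also assumed: a standard normal severity score S; a latent survival variable with correlation ρ to S; log ventilator time = log 14 + b·S + noise. IgG has no effect on ventilator time.

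**Closed form.** The mean of S among survivors is −ρ·φ(z)/p, where p is the survival probability and z its normal quantile.
- p = 0.25: φ(−0.674)/0.25 = 0.318/0.25 = 1.271
- p = 0.50: φ(0)/0.50 = 0.399/0.50 = 0.798
- difference in mean S, high minus low IgG: ρ × (1.271 − 0.798) = 0.473ρ
- ratio of geometric mean ventilator time, high/low: exp(0.473·b·ρ)

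The share of variance in log time due to severity is b²/(b² + SD²).

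| b, noise SD | Share | Ratio at ρ = 0.3 | Ratio at ρ = 0.9 | False positives at 0.3% (simulated, ρ = 0.3 to 0.9) |
|---|---|---|---|---|
| 0.5, 0.40 | 0.25/0.41 = 61% | exp(0.071) = 1.07 | exp(0.213) = 1.24 | about 0.5% to 5% |
| 0.3, 0.57 | 0.09/0.415 = 22% | exp(0.043) = 1.04 | exp(0.128) = 1.14 | about 0.5% to 1.1% |
| 0.2, 0.61 | 0.04/0.412 = 10% | exp(0.028) = 1.03 | exp(0.085) = 1.09 | about 0.4% to 0.6% |

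The false-positive rates come from linear regression of log time on IgG in survivors. In the first row, ρ = 0.5 and 0.7 give ratios of 1.13 and 1.18, with false-positive rates of about 1.0% and 2.3%. Nearly all false positives point to longer ventilation at high IgG. At ρ = 0 the ratio is 1.00 and the error rate is nominal.

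**Cross-check by a different model.** Suppose 25% of patients survive at either IgG level and a further 25% survive only at high IgG. Let r be the ventilator time of the second kind relative to the first, and e the true effect in every patient. Half the high-IgG survivors are of the second kind, so the ratio is e × r^0.5. The error rates below are simulated at 0.003125 in the wrong direction, with an assumed log-SD of 0.6.
- e = 1: r = 1, 1.25, 1.5 and 2 give ratios of 1.00, 1.12, 1.23 (closed form 1.225) and 1.41; error rates are 0.4%, 1.6%, 5.5% and 25%.
- e = 0.85 (a true 15% shortening): ratios are 0.85, 0.95, 1.04 and 1.20. The sign reverses when r exceeds 1/0.85² = 1.38.

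The strongest case in the table (1.24) corresponds to r = 1.24² = 1.54, so r = 2 is a more extreme assumption than any in the table.

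**Do items 6 and 13 repair it?** With death scored as zero ventilator-free days over 28 days (a convention the plan does not state), the e = 1 scenarios favour high IgG by 1.6 to 3.6 days. With no rule for deaths, raw durations in item 6 are cut short by early deaths. Those are commoner at low IgG, so the pull is in the same direction as item 12.

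**The case against.** The strongest reply is that item 12 is one of 16 secondary endpoints, does not touch the primary analysis, and has two unrestricted ventilation measures beside it. The bias also depends on an unproven link. If severity explains about 10% of the variance in ventilator time, the error rate at 0.3% stays near nominal. If the saved patients ventilate as long as other survivors, the bias is zero. All of this stands. It limits the size of the problem but does not make the comparison sound.

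Some stronger readings are tempting, and the documents do not support them.
- A reader might infer that ventilator time is analysed only in survivors. Items 6 and 13 carry no such restriction, and Section 3.1 assigns models to both.
- A reader might infer that the Group A ICU endpoints exist only for patients who enter the ICU after transfusion, or that ICU mortality is confined to ICU entrants. The Initial Data Collection Form allows ICU as the status at enrolment, and Section 3.1 nowhere confines ICU mortality to entrants. The denominator is simply unstated.
- A reader might infer that conditioning in the ICU and readmission endpoints also makes plasma appear to prolong ventilation. It cannot. Readmission is possible only after discharge alive, which is a separate selection issue. Every participant receives plasma, so all these comparisons are by antibody level and not against an untreated group.

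**Conclusion.** The point holds for Group B item 12. As written, it is a tested comparison among patients selected by the primary outcome. With the planned 25% and 50% survival and no true effect on ventilation, the survivor-only ratio is about 1.03 to 1.24. The false-positive rate at 0.3% runs from near nominal to about 5%. Both depend on how strongly severity drives ventilator time and survival. The two-stratum model gives larger values if saved patients ventilate twice as long as other survivors. The IgG distribution, the variances and the severity links are assumptions, because the documents give none. The direction requires only that sicker patients both die more often and ventilate longer; without that link there is no bias. Items 6 and 13 are not a clear safeguard while the handling of deaths is unstated. For ICU mortality and readmission the gap is an unstated denominator and no rule for death, not a demonstrated bias.

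**What to change.** 1. Replace the test of item 12 with time from transfusion to liberation from ventilation in all Group B patients, with death as a competing event. Report cumulative incidence, with cause-specific and subdistribution models in IgG read together. Tabulate survivor-only times without a test, and state to what date survival is counted.
2. Define ventilator-free days with an explicit score for deaths and a fixed window, for example zero days for a death within 28 days. State how deaths enter duration of respiratory support, ICU stay and total stay.
3. Analyse ICU death with all treated patients as the denominator.
4. Treat death as a competing event for readmission, using the deaths already recorded (in hospital and to day 28). A 90-day composite of readmission or death is suitable only if deaths after discharge are captured. Section 2.2 describes a day-28 call and 90-day tracking of readmission, but not of deaths after day 28.

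Cost: items 1 to 3 are analysis-plan wording and slightly more analysis, since ventilator status is recorded daily to discharge and death is recorded. The composite in item 4 could require added follow-up. The price is a less direct summary of ventilator duration: measures that count deaths mix survival with weaning and should be described that way.
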